3.1 Safety Monitoring

Participants will be monitored by hospital personnel as per protocol. Clinical adverse events (AEs) will be reviewed daily through to discharge or the end of the treatment period. Safety monitoring will also include laboratory assessment of hematology, chemistry and ECG as per the Schedule of Events. Serum trough levels of GLS-1027 will be assessed at select times throughout the trial as per the Schedule of Events. Participants will also be followed for up to 56 days post-enrollments for health status and adverse events.

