6.1.3 Day 2 through 29 (or until discharge or death)

- Administer study drug with AM medications if calculated creatinine clearance is \geq 60.
- Determine and record WHO COVID-19 classification level (Appendix B)

- Review new concomitant medications
- Record past 24 hour maximal and minimal temperature (°C), respiratory rate, heart rate, systolic and diastolic BP
- Record potential co-morbid complications of SARS-CoV-2 infection to include shortness of breath, arterial thrombosis (myocardial infarction, stroke, peripheral blood clot), mental confusion, death
- Record adverse effects
- Collect and Record labs as indicated in the Schedule of Events: CBC, BMP, LFTs, CRP, ferritin, D-dimer, CPK, IL-6
- Record if care given in ICU setting
- Record ventilatory status: O₂ use, CPAP use, ventilator, ECMO
- Record O₂ flow rate, FiO₂ % (if intubated), CPAP pressure (as relevant), PEEP setting (as relevant)
- Perform ECG (12 lead) on day 2 at 75-90 minutes post dose, and on day 15 ± 2 days
- Collect serum for CPK and GGT (Day 7) and, if abnormal, then weekly until values normalize
- Collect blood for plasma for GLS-1027 trough measurement as indicated in the Schedule of Events
- Collect blood for serum and PBMCs as indicated in the Schedule of Events
- Pharmacy to review patient creatinine and calculated creatinine clearance daily.

6.1.4 Day 56

- Review medical record to document date of discharge or death, as relevant
- Determine and record WHO COVID-19 classification level (Day 56)
- If hospitalized, review chart to document intercurrent AEs
- If not hospitalized, query participant to document intercurrent AE's from the end of the primary study period

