9.6.1 Study Reporting Period of Adverse Events

All AEs will be recorded throughout the study and the 28 day follow-up period.

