Record if mechanically ventilated and level of PEEP, % FiO ₂ h	X	X	Х	X	X	X	Х	X	Х	X	X	X	Х	X	X		
Record if treated by ECMO	X	Х	X	X	X	X	X	X	X	X	X	X	X	X	Х		
Record admission ECG	Х																
Study Related Procedures																	
Administer assigned study drug ¹	Х	Х	X	Х	X	Х	Х	Х	X	Х	Х	X	Х	Х			
Perform urine pregnancy test	Х																
Perform ECG (12-lead) J		Х					Х										
Collect serum for CPK, GGT k	Х						Х										
Collect blood for plasma for PK assessment ¹		Х															
Collect blood for plasma for trough drug measurement (AM blood draw)		Х	Х	Х			Х										
Collect blood for serum (10mL red top,3 tubes)	Х						Х							Х			
Collect blood for PBMCs (10mL ACD; 3 tubes) ⁿ	Х						Х							Х			
Blood volume for serum, PBMCs	60						70							60			_

^a Vital signs to be recorded daily to include: temperature, respiratory rate, heart rate, systolic and diastolic blood pressure

CONFIDENTIAL Page 7 03DEC2021

^b Hematology labs to be recorded (as collected as part of clinical care) and recorded: Hemoglobin, hematocrit, platelets, neutrophils, band forms, lymphocytes, eosinophils

^c Basic metabolic panel labs: Sodium, potassium, creatinine, BUN, glucose, liver function tests; LFTs include AST, ALT, bilirubin (direct), alkaline phosphatase, LDH, albumin.

^d Other labs to be recorded if performed: Ferritin, CRP, IL-6, troponin, D-dimer

^e Procalcitonin: record only initial measurement or within 48 hours of admission and/or SARS-CoV-2 diagnosis (may be performed prior to date of enrollment)

f Record maximal daily level of O2 by nasal cannula prescribed, if participant is receiving O2 by nasal cannula

^g Record maximal daily level of end expiratory pressure delivered by CPAP prescribed, if participant is receiving CPAP

- ⁱ Study drug administration will commence on the day of enrollment if treatment can be administered before 10 pm and then with AM medications thereafter, If, study drug cannot be administered prior to 10 pm on the day of enrollment, then the 1st day of treatment will occur on the day after enrollment.
- ^j Perform a 12-lead ECG on the 2nd day of treatment with study drug between 75 and 90 minutes post-administration on day 2; and on day 15 (± 2 days)
- ^k Serum is collected for CPK and GGT on day 1 and day 7, and weekly thereafter, if values on day 7 are abnormal until return to normal

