9. SAFETY ANALYSES

All safety analyses will be based on the Safety Population.

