9.1. Adverse Events

An adverse event (AE) is defined as any unfavorable and unintended change in the structure, function, or chemistry of the body, or worsening of a pre-existing condition, temporally associated with the use of a product whether or not considered related to the use of the product. In this study, such changes will be monitored, classified, and summarized, as Clinical or Laboratory AEs. Medical conditions/diseases present before starting the investigational drug will be considered adverse events only if they worsen after starting study treatment. Verbatim terms on CRFs will be mapped to preferred terms (PTs) and system organ classes (SOCs) using the Medical Dictionary for Regulatory Activities (MedDRA) (version 23.0).

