9.1.5. Summaries of Adverse Events

An overall summary of AEs will display, by treatment, the number and percentage of subjects who had any TEAE, whose strongest TEAE relationship to study drug is related or not related, whose maximum TEAE severity is mild, moderate, or severe, who had any SAE, any Serious TEAE, any TEAE leading to study discontinuation, and any TEAE leading to death.

The following summaries (number and percentage of subjects) of AEs (by SOC and PT) will be provided by treatment:

- All TEAEs
- All TEAEs by strongest relationship
- All TEAEs by maximum severity grade
- All Related TEAEs by maximum severity grade

CONFIDENTIAL Page 14 03DEC2021

- All Serious AEs
- All Serious TEAEs
- All TEAEs leading to study discontinuation
- All TEAEs leading to death

These summaries will present the number and percentage of subjects with at least one qualifying AE. Subjects may have more than one AE per SOC and PT. Each summary will be ordered by descending order of incidence of SOC and PT within each SOC.

In addition to the by-treatment summaries, data listings will be provided for the following:

- All AEs (with a flag indicating whether the event is treatment emergent)
- SAEs
- AEs leading to study discontinuation
- Deaths

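### Laboratory adverse-event percentages ignore how long labs were observed, so an arm discharged sooner shows fewer events at the same daily risk, by an amount the documents cannot fix

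*SAP*

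**What the plan says.** - **Percentages.** SAP 9.1.5: "These summaries will present the number and percentage of subjects with at least one qualifying AE". SAP 9: "All safety analyses will be based on the Safety Population". That population is everyone randomised who took at least one dose.
- **What counts.** SAP 9.1: "In this study, such changes will be monitored, classified, and summarized, as Clinical or Laboratory AEs". SAP Appendix B has no separate laboratory-event table, so these events appear as preferred-term rows and inside the any-event row.
- **Window.** Protocol 9.6.1: "All AEs will be recorded throughout the study and the 28 day follow-up period". The treatment-emergent definition in SAP 9.1.4.1 has no end date.
- **In hospital.** Protocol 3.1 says clinical events "will be reviewed daily through to discharge or the end of the treatment period". Protocol 6.1.3 puts laboratory collection in a visit block that ends at discharge or death. SAP Table 1 has no routine laboratory row after Day 15, and its footnote b takes haematology from routine care. The one extension is weekly repeat of CPK and GGT if abnormal on Day 7.
- **After discharge.** Protocol 6.1.4: "If not hospitalized, query participant to document intercurrent AE's from the end of the primary study period". SAP Table 1 footnote m adds telephone contact at Days 28 and 56. No routine blood draw is scheduled for discharged patients.
- **Shift tables.** SAP 9.2 uses the worst post-baseline value. The footnote to Table 14.3.4.3 divides by patients with a baseline and a post-baseline result. That denominator is narrower, but it too ignores how many results each patient had.

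**The concern.** A rise in transaminases or a fall in neutrophils without symptoms is found only if blood is taken. A patient discharged on Day 6 offers fewer chances of detection than one discharged on Day 14, yet each counts as one person in the denominator. The percentages are comparable across arms only if laboratory observation is similar across arms. The trial hopes to reduce clinical worsening, so an effective arm may well go home sooner. Its laboratory-event rows would then look better with no change in daily risk, and a real increase in daily risk could be partly masked. This is relevant here: Protocol 1.1.2 reports neutropenia in two Phase I subjects, and Protocol 7.3.2 sets neutrophil and transaminase thresholds for halting drug. No planned table sets adverse events against observed time.

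**Working it through.** **Inputs from the documents.** Failure 50% on placebo and 25% on active (Protocol 8.2); 44 per arm. Post-baseline laboratory days: Protocol Table S2, haematology and chemistry on Days 2–7, 14, 21, 28; SAP Table 1, haematology on Days 2, 3, 6, 9, 12, 15 and liver tests on Days 6, 9, 12, 15.

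**Not in the documents.** Length of stay, laboratory-event rate and daily hazard. There is no plan figure to reproduce, and everything below is assumed, with equal daily risk in both arms.

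**1. One stay per arm, constant hazard.** With placebo risk p0 and stays T0 (placebo) and T1 (active), apparent reduction = 1 − [1 − (1 − p0)^(T1/T0)] / p0. For p0 = 10% and 10 v 8 days: 0.9^0.8 = 0.919, active risk 8.1%, reduction 19.2%.

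| Placebo risk | Stay 15% shorter | 20% shorter | 25% shorter |
|---|---|---|---|
| 10% | 14.3% | 19.2% | 24.0% |
| 30% | 12.8% | 17.3% | 21.8% |
| 50% | 11.0% | 14.9% | 18.9% |

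The percentage falls roughly in proportion to the stay, less so when events are common.

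**2. Stay linked to failure.** Risk = (1 − pf)(1 − e^(−h·Ln)) + pf(1 − e^(−h·Lf)), where pf is the failure rate and Ln, Lf are the stays of non-failures and failures. With h = 2%/day, Ln = 7, Lf = 15:
- placebo: 0.5 × 0.1306 + 0.5 × 0.2592 = 19.5%
- active: 0.75 × 0.1306 + 0.25 × 0.2592 = 16.3%
- reduction: 16.5%

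Over Ln 4–12 days, Lf 12–28 days (Lf > Ln) and h 0.5–5%/day, the reduction runs from 3.4% (10 and 12 days, 5%/day) to 36.8% (4 and 28 days, 0.5%/day). With Lf at most 15 days, the SAP laboratory window, the top is 28.5%.

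**3. Scheduled draws only, 5% detection per draw.** For stays of 7 and 15 days, SAP haematology gives 3 and 6 draws: 1 − 0.95^3 = 0.143, 1 − 0.95^6 = 0.265; placebo 20.4%, active 17.3%, ratio 0.85. Over stay pairs 5/15, 7/15, 7/20 and 6/12 days the null ratio active/placebo is:
- SAP haematology days: 0.77–0.89
- SAP liver-test days: 0.71–0.76, and 0.50 for 5/15, because a 5-day stay contains no post-baseline liver-test day
- Protocol days: 0.88–0.97

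**4. Front-loaded hazard.** Let the hazard decay at 0.1–0.3 per day, with placebo risk 20% over 10 days. A stay of 8 days then lowers the percentage by only 11.7% down to 3.9%.

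**5. Any-event row.** If a share q also has a clinical event seen equally in both arms, risk = 1 − (1 − q)(1 − p). For p0 = 30%, q = 40% and a 20% shorter stay: 58.0% v 54.9%, a 5.4% reduction. Over q = 20–60%, p0 = 10–50% and stays 15–25% shorter, it is 0.9–12.6%.

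**6. What a rate does.** In the step 2 example, mean days to first event or discharge, (1 − e^(−hL))/h averaged over the mix, are 9.75 and 8.14. The rates are 0.1949/9.75 and 0.1628/8.14, both 2.0 per 100 patient-days, ratio 1.00. In step 4 with decay 0.3, cumulative hazard at 8 days is (1 − e^(−2.4))/(1 − e^(−3.0)) = 0.957 of that at 10 days, so average hazard per in-hospital day is 0.957 × 10/8 = 1.20 times placebo. The rate then over-corrects.

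**7. Precision.** In the step 2 example, expected patients with an event are 44 × 0.195 = 8.6 and 44 × 0.163 = 7.2. Taking 9 and 7, the SE of the log rate ratio is √(1/9 + 1/7) = 0.504, so the 95% CI is the estimate multiplied and divided by about 2.7.

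**The case against.** A reader might infer that the drug would look some 15–25% safer overall, or that the primary safety comparison is compromised. The documents support neither. A figure of that order restates an assumed shortening of stay of the same size, with uncommon events and a constant hazard. It concerns laboratory events only. The primary safety outcome is the incidence of serious events, which Protocol 7.1.2 collects to the final visit in or out of hospital.

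Other points against:

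- *Failure is not the same as a long stay.* The composite includes withdrawal, transfer, salvage therapy and stopping drug, and some of these shorten observation. This stands: the stays in step 2 are illustrations, and the gap could be smaller or reversed.
- *The trial targets failure, not length of stay.* Days of hospitalisation is absent from Protocol 2.3 and only exploratory in SAP 8.3. This stands: the bias is conditional on stays differing.
- *Part of this is already reported.* Laboratory values are summarised by study day with n (Table 14.3.4.1), as are exposure (Table 14.1.5) and hospital days (Table 14.2.2.8). This helps, but by-day summaries describe only those still being sampled and give levels rather than events. The other tables are not linked to event counts.
- *Crude percentages are conventional in a small descriptive safety table.* This stands, and is why they should stay.
- *A rate has its own faults.* It can over-correct (step 6), it counts in-hospital days when drug is halted, and it is imprecise (step 7). This stands, and it limits the remedy's scope and use.

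**Conclusion.** The mechanism and its direction hold: laboratory events are counted without regard to observation time, labs are observed essentially only in hospital, and an arm with shorter stays will tend to show lower percentages at equal daily risk. The size cannot be determined from the documents. Under assumed stays and hazards, with detection throughout the stay, the apparent reduction for laboratory events is roughly 3–37%. It is smaller if risk is front-loaded or if only the protocol's scheduled draws detect events, and can be larger where short stays contain no scheduled draw. The any-event row moves by about 1–13% under the assumptions in step 5. None of these figures applies to serious events or deaths. Mild clinical events may also be affected, since daily review gives way to one or two later contacts, but that was not quantified. This is a worthwhile addition to the safety tables, not a flaw in the primary safety outcome.

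**What to change.** Keep every planned percentage. For laboratory events only, add one table by arm on the Safety Population:

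1. In-hospital patient-days of laboratory observation, from first dose to the earliest of discharge, death or Day 15.
2. Patients with a first event per 100 such patient-days, with time stopped at the first event, and the rate ratio with 95% CI for each dose against placebo.
3. The percentage with a first event in a common early window, for example first dose to Day 7, with the number still in hospital at its end.

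List before unblinding the preferred terms that count as laboratory events, since the SAP classifies them but gives them no separate output. The Day 15 limit follows SAP Table 1. Protocol Table S2 lists later laboratory days, so the SAP should state which schedule governs.

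The cost is modest programming from first-dose, event-start and discharge dates already collected, with no new data. The drawback is interpretive. Intervals will be wide at 44 per arm. The rate assumes a roughly constant hazard and can over- or under-correct if detection is front-loaded or late days belong to sicker or off-drug patients. It should be labelled descriptive and read beside the percentages.

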9.2. Clinical Laboratory Evaluations

Continuous response variables per time point will be summarized with mean, median, minimum, and maximum values. Categorical response variables will be summarized per time point with percentages. Shift from baseline in laboratory parameter results (indicated as Low, Normal, or High) will be summarized for the worse (most extreme) post-baseline assessment. Mean (+/- SD) laboratory parameter values of interest will be graphically presented over time by treatment. All laboratory parameters will be listed and include indicators for low/high and clinical significance as determined by the investigator.

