Record Hematology ^b	Х	Х	Х	Х	Х	Х	Х							Х							Х							Х		
Record Basic Metabolic Panel, LFTs °	Х	Х	Х	Х	Х	Х	Х							Х							Х							Х		
Record other labs ^d (for days available)	Х	Х	Х	Х	Х	Х	Х	Х	Х	Х	Х	Х	Х	Х	Х	Х	Х	Х	Х	Х	Х	Х	Х	Х	Х	Х	Х	Х	Х	
Record Procalcitonin (baseline value) ^e	Х																													
Record admission CXR	Х																													
Record if care given in ICU setting	х	Х	Х	х	Х	х	Х	Х	Х	х	х	х	х	х	Х	Х	Х	Х	Х	Х	Х	х	х	Х	Х	х	х	х	х	
Record whether nasal O ₂ prescribed and dose level (L/min) ^f	х	х	х	х	х	х	х	х	х	х	х	х	х	х	х	х	х	х	х	х	х	х	х	х	х	х	х	х	х	
Record whether CPAP prescribed and expiratory pressure ^g	х	х	х	х	х	х	х	х	х	х	х	х	х	х	х	х	х	х	Х	Х	Х	х	х	х	х	х	х	х	х	
Record if mechanically ventilated and level of PEEP, % FiO ₂ ^h	х	х	Х	х	х	х	х	х	х	х	х	х	х	х	х	х	х	х	х	Х	Х	х	х	х	х	х	х	х	х	
Record if treated by ECMO	Х	Х	х	х	х	х	Х	Х	Х	х	х	Х	х	х	Х	Х	Х	Х	Х	Х	Х	х	х	Х	Х	х	х	Х	х	
Record admission ECG	Х																													
Study Related Procedures																														
Administer assigned study drug ⁱ	Х	Х	Х	Х	Х	Х	Х	Х	Х	Х	Х	Х	Х	Х	Х	Х	Х	Х	Х	Х	Х	Х	Х	Х	Х	Х	Х	Х	(X)	
Perform urine pregnancy test	Х																													
Perform ECG (12-lead) ^j		Х													Х															
Collect serum for CPK, GGT ^k	Х					l	Х		l			l					l	l				Ī				l		l		
Collect blood for plasma for PK assessment ¹		Х																												
Collect blood for plasma for trough drug measurement (AM blood draw)		х	х	х					х							х							х					х		

GLS27-005

GeneOne Life Science, Inc.

Clinical Protocol

Collect blood for serum (10mL red top,3 tubes)	Х		Х		Х				Х				Х			Х	
Collect blood for PBMCs (10mL ACD; 3 tubes)	Х		Х		Х				Х				Х			Х	
Blood volume for serum, PBMCs	60		60	5	60				60				60			60	

^a Vital signs to be recorded daily to include maximal and minimal: temperature, respiratory rate, heart rate, systolic and diastolic blood pressure

^b Hematology labs to be collected as necessary and recorded: Hemoglobin, hematocrit, platelets, neutrophils, band forms, lymphocytes, eosinophils

^c Basic metabolic panel labs to be collected as necessary and recorded: Sodium, potassium, CO₂ (bicarbonate), creatinine, BUN, glucose, liver function tests (LFTs) that should be recorded include AST, ALT, bilirubin (direct), alkaline phosphatase, LDH, albumin. These labs are performed daily per the hospital COVID algorithm.

^d Other labs to be recorded as available: Ferritin, CRP, IL-6, troponin, D-dimer

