1.1.2 Human experience with GLS-1027

GLS-1027 has completed two Phase I safety and pharmacodynamic studies: CAT-001 (NCT00627120) and CAT-002 (NCT00760396). The compound was then called VGX-1027. Both human clinical studies, as well as pre-clinical pharmacokinetic (PK) studies, were published together in 2016 by Lee et al. ^[11]. More detailed information regarding these clinical trials is presented in the GLS-1027 Investigator's Brochure.

CAT-001 was a single-ascending dose study of GLS-1027. Six subjects each received single doses of drug at 0, 1, 10, 100, 200, 400, and 800 mg in a fasted state with 72-96 hours between administration of successive doses. An additional sub-study was conducted to determine PK of a 100 mg dose given in a fasted or fed state. CAT-002 was a multiple-ascending dose study of GLS-1027 administered at doses of either 0, 40, 100,

200 mg daily, or 200 mg twice daily over a 5-day period. Adverse events and PK were assessed during the trial.

Overall, in the multiple ascending dose study, 15 of the 40 subjects experienced one or more adverse events. Among those receiving study drug, grade 1 hypertension was observed in 4 subjects at each of the three highest doses of 100, 200, and 200 mg BID. Each of these subjects had borderline elevations in systolic blood pressure (>145). Additionally, two subjects in the single ascending dose study (100, 200 mg) experienced neutropenia. Both subjects were of African American ethnicity and had low baseline neutrophil counts. Headache was observed in two individuals in the multiple dose study (200, 200 mg BID). Hypersomnia was observed in two individuals in the single dose study who received 10 mg of GLS-1027, however, it was also observed in two placebo subjects in the single dose study.

The pharmacokinetic profile of GLS-1027 showed proportionate increases in peak serum concentration and AUC relative to dose with normalized C_{max} of approximately 60 µg/L/mg and normalized AUC of 450-500 µg-hr/L/mg. Serum C_{max} and AUC was increased by a factor of approximately 1.4-1.5 in the fed state. The serum half-life was approximately 7 hours with no drug accumulation observed over the 5-day period at any dose level. Drug was highly bioavailable with 90% excreted unchanged in the urine. Separate pre-clinical toxicology studies showed no evidence of hepatic metabolism or interaction with the cytochrome P_{450} enzymes.

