7.1.6 Abnormal Laboratory Values

Laboratory abnormalities will be classified according to the CTCAE v5:

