3. STUDY DESIGN AND PLAN

This is a Phase II, randomized, double-blind, placebo-controlled study to assess 2 dose levels of GLS-1027 for the prevention of treatment failure among participants admitted to the hospital with PCR confirmed infection with SARS-CoV-2 (WHO classification 3 or 4). Subjects can be enrolled up to 72 hours from the time of hospital admission.

Participants will be randomized to placebo or GLS-1027 at either 120 mg or 360 mg daily in a 1:1:1 ratio as adjunctive to standard of care based on the hospital COVID-19 treatment algorithm and/or local COVID-19 treatment practices. Participants will be administered study drug for a maximum treatment period of 14 days or until discharge or death, whichever comes first. Primary outcome will be assessment at day 28, with follow-up to continue to Day 56 to document AEs and outcome as to discharge, death, or WHO COVID-19 classification level if subject remains hospitalized.

All subjects will be considered to have completed the study except for the following circumstances:

- Withdrawal of consent from study
- Loss to follow-up
- Stopped study treatment for any reason other than discharge, pregnancy, or decreased renal function

Table 1: Schedule of Assessments

Tests and Observations	1	2	3	4	5	6	7	8	9	10	11	12	13	14	15	28	56 ^m
Clinical Evaluations																	
Obtain written Informed Consent	Х																
Confirm Eligibility Criteria	Х																
Demographics	Х																
Medical History	Х																
Concomitant Medications	Х	Х	Х	Х	Х	Х	Х	Х	Х	Х	Х	Х	Х	Х	Х	Х	Х
Review Medical Record	Х	Х	Х	Х	Х	Х	Х	Х	Х	Х	Х	Х	Х	Х	Х	Х	Х
WHO COVID-19 Classification (Appendix B)	Х	Х	Х	Х	Х	Х	Х	Х	Х	Х	Х	Х	Х	Х	Х	Х	Х
Safety Evaluations																	
Record Adverse Events	Х	Х	Х	Х	Х	Х	Х	Х	Х	Х	Х	Х	Х	Х	Х	Х	Х
Record AM Vital Signs a	Х	Х	X	Х	Х	Х	Х	Х	Х	Х	Х	Х	Х	Х	Х		
Record Hematology ^b	Х	Х	Х			Х			Х			Х			Х		
Record Basic Metabolic Panel ^c	Х	Х	Х	Х	Х	Х	Х	Х	Х	Х	Х	Х	Х	Х	Х		
Record liver function studies (LFTs) °	Х					Х			Х			Х			Х		
Record other labs ^d (for days available)	Х	Х	Х	Х	Х	Х	Х	Х	Х	Х	Х	Х	Х	Х	Х		
Record Procalcitonin (baseline value) e	Х																
Record admission CXR	Х																
Record if care given in ICU setting	Х	Х	Х	Х	Х	Х	Х	Х	Х	Х	Х	Х	Х	Х	Х		
Record whether nasal O ₂ prescribed and dose level (L/min) ^f	Х	Х	Х	Х	Х	Х	Х	Х	Х	Х	Х	Х	Х	Х	Х		
Record whether CPAP prescribed and expiratory pressure ⁹	X	X	X	X	Х	Х	X	Х	Х	X	Х	Х	X	Х	X		

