9.3. Vital Signs

Vital signs (temperature, heart rate, systolic blood pressure (SBP), diastolic blood pressure (DBP)) will be summarized using descriptive statistics (sample size, mean, SD, median, minimum, and maximum) at baseline and at each post-baseline time point by treatment. Change from baseline will also be summarized at each post-baseline time point. Mean (+/- SD) vital sign values will be graphically presented over time by treatment. All vital signs results will be listed.

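### The SAP's laboratory shift tables cannot show how many subjects worsened from an already low baseline or reached the protocol's own thresholds, and the SAP disagrees with itself on which daily blood pressure is analysed

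*SAP*

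**What the plan says.** **Phase I background.** Protocol 1.1.2 reports that in the multiple-dose study "grade 1 hypertension was observed in 4 subjects at each of the three highest doses". In the single-dose study two subjects had neutropenia, and both "had low baseline neutrophil counts".

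**Laboratory data.** Protocol 7.1.6 states: "Laboratory abnormalities will be classified according to the CTCAE v5". Protocol 6.3 sends chemistry and blood counts to the same grading, and 7.1.4 has the investigator grade laboratory adverse events on that scale. Protocol 7.3.2 sets laboratory levels at which study drug is halted: neutrophils below 1000, ALT or AST at 20 times ULN or more, and bilirubin at 5 or 10 times ULN depending on baseline. SAP 9.2 asks for continuous summaries at each time point, and then: "Shift from baseline in laboratory parameter results (indicated as Low, Normal, or High) will be summarized for the worse (most extreme) post-baseline assessment". Tables 14.3.4.3 and 14.3.4.4 follow that wording.

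**Blood pressure.** Protocol Table S2, footnote a, reads: "Vital signs to be recorded daily to include maximal and minimal: temperature, respiratory rate, heart rate, systolic and diastolic blood pressure". Protocol 6.2.3.3 agrees. The matching row of SAP Table 1 is "Record AM Vital Signs", and its footnote no longer mentions maximum or minimum. Listing 16.2.8.3 nevertheless has minimum/maximum columns for systolic and diastolic pressure. SAP 9.3 plans descriptive statistics by day and adds: "Change from baseline will also be summarized at each post-baseline time point". Neither 9.3 nor Table 14.3.4.5 says which reading of the day is used.

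**The concern.** The protocol itself names two findings from earlier human exposure. One would expect the safety tables to show, by arm, how many subjects had each and how badly. A three-category shift does this poorly for neutropenia, because the Phase I cases started low and the low category has no further step. It does it poorly for liver tests, because everything above ULN is one category.

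For blood pressure, two programmers could build Table 14.3.4.5 from different readings and each point to the SAP for support. At stake is whether a dose-related worsening can be read from the by-arm tables or has to be pieced together from listings. SAE incidence, the safety part of the primary objectives, is not affected.

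**Working it through.** The plan states no figure to reproduce. The check sets its sections against one another and asks what each table can show.

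**1. What the shift table can separate.** Assume a site's lower limit of normal for neutrophils lies above 1000.

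| Baseline | Worst post-baseline | Cell |
|---|---|---|
| Neutrophils just below normal | unchanged | Low to Low |
| Neutrophils just below normal | below 1000 (7.3.2 level) | Low to Low |
| ALT normal | just above ULN | Normal to High |
| ALT normal | 20 × ULN (7.3.2 level) | Normal to High |
| Bilirubin above normal | 10 × ULN (7.3.2 level) | High to High |

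In each pairing the milder and the more serious course share a cell. For ALT, one cell spans a range of 20/1 = 20-fold. The 10 × ULN bilirubin level applies only to subjects already above normal, so with that high reading taken as the worst value it can never register as a shift.

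**2. Direction.** A subject with one high and one low post-baseline neutrophil count has two candidates for the most extreme value. SAP 9.2 and the table shells do not say which one counts.

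**3. Whether the continuous tables fill the gap.** Tables 14.3.4.1 and 14.3.4.2 give n, mean (SD), median, minimum, maximum and change by day. Suppose all 44 subjects in an arm have a value on a day, the minimum is below 1000 and the median is not. From those two figures, one subject could be below 1000. So could 21, because the 22nd and 23rd ordered values, which fix the median, would still be at or above 1000. Mean and SD narrow this but do not give the count. Subjects also reach their lowest values on different days, so the daily columns cannot be combined into a number of subjects affected.

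**4. Whether other tables count the thresholds.** SAP 9.1.5 tabulates events leading to study discontinuation, not to drug interruption. Table 14.1.5 counts missed doses without reasons. Listing 16.2.5.2 gives reasons, but a listing is not a by-arm count. By contrast, SAP 9.4 does count subjects above QTcF cut-offs, so the format is already in use.

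**5. Blood pressure: how much a mean can absorb.** This is an illustration only; the rises and SDs are assumptions, not document figures.

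- Shift in arm mean = k × rise / 44. For k = 2 and 20 mmHg: 2 × 20 / 44 = 0.9. For k = 4 and 40 mmHg: 4 × 40 / 44 = 3.6. For k = 8 and 40 mmHg: 8 × 40 / 44 = 7.3.
- Standard error of a difference between two arms of 44 = SD × √(2/44). For SD 12, 15 and 20: 2.6, 3.2 and 4.3 mmHg.

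Two to four affected subjects therefore move the mean by 0.9 to 3.6 mmHg against a standard error of 2.6 to 4.3. A small cluster can be lost in daily means whichever reading is used. Eight subjects with the larger rise would be harder to miss.

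**The case against.** The strongest reply is that the SAP does what the protocol's analysis section asks. Protocol 8.5.2 calls for continuous summaries and a shift from baseline, with no table of grades. SAP 9.2 supplies these and uses the worst value rather than the last assessment, which is more sensitive. This stands: a reader might infer that Protocol 7.1.6 obliges the sponsor to produce grade-shift tables, but it says how abnormalities are classified, not how they are tabulated.

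A reader might also infer that laboratory values appear solely as Low, Normal or High. They do not: the continuous tables include minimum, maximum and change from baseline, so a further fall in a low subject does enter them. Step 3 shows what is still missing.

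Nor do the documents support saying that the signals are hidden. Treatment-emergent events are tabulated by arm, preferred term and maximum CTCAE grade, and the Phase I hypertension was itself reported as a graded adverse event. The limit is that this route needs the investigator to report an event, and Protocol 7.1.1 excludes laboratory abnormalities considered non-significant.

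On blood pressure, a reader might infer that the SAP averages a morning value in place of the daily maximum, or that morning readings are pre-dose troughs. SAP 9.3 names no reading, and nothing says that the morning reading precedes the dose. The systolic level of 145 in Protocol 1.1.2 describes the Phase I cases and is not a threshold of this trial. Finally, the SAP is written to protocol version 5.0, while the supplied protocol differs from it elsewhere (28 against 14 days of treatment). Morning vital signs may be the current rule and the listing a leftover.

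**Conclusion.** The point holds in two parts.

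**Laboratory.** The one subject-level categorisation cannot show worsening from an already abnormal baseline in the same direction, does not separate mild from severe abnormality, and fixes no direction for two-sided tests. No laboratory table uses the CTCAE grades or counts subjects at the Protocol 7.3.2 levels. This follows from the text and the table shells; the neutrophil example assumes only a lower limit of normal above 1000. It is a worthwhile and inexpensive improvement, not a breach of Protocol 8.5.2.

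**Blood pressure.** The SAP contradicts itself, and the analysed reading is undefined. Which way to resolve this depends on what version 5.0 collects, which the supplied documents do not settle. The dilution figures rest on assumed rises and SDs and show only that daily means are a weak tool for a few affected subjects.

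No stated power, alpha or sample-size figure changes.

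**What to change.** **(a) Laboratory.** In Tables 14.3.4.3 and 14.3.4.4, replace or supplement the three-category shift with baseline-to-worst CTCAE v5 grade shifts. Define worst by direction for each test: the lowest value for neutrophils, and separate low and high shifts where both matter. Add a by-arm count of subjects reaching each laboratory threshold already in Protocol 7.3.2. This counts events against existing rules and changes none of them.

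**(b) Blood pressure.** Reconcile SAP Table 1 and its footnote a, SAP 9.3, Table 14.3.4.5 and Listing 16.2.8.3 with the protocol version in force, and state which daily reading is analysed. Where the daily maximum is collected, summarise maximum systolic and diastolic pressure by arm and add a by-arm count by CTCAE hypertension grade.

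**Cost.** Part (a) needs SAP wording and a few more tables from values already planned for collection. Grading needs site normal ranges, which the Low/Normal/High flags already require. Part (b) is wording and programming if the maximum is collected. If version 5.0 collects only a morning reading, the SAP should say so, drop the minimum/maximum columns and acknowledge the limitation; obtaining a daily maximum would then be a change to data collection.
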